- To evaluate the safety and efficacy of long-term use of lorecivint in subjects with knee OA

- Safety
- ≡ Clinical assessments
- ≡ X-ray
- ▼ Biomarkers

* X-ray is performed at Week 52 of the parent study; some clinical assessments and biomarker collection are performed at Week 56 (EOS) of the parent study.

+ Study injections are to occur every ~52 weeks until termination.

Abbreviations: EOS = End of Study; LOR = lorecivint; OA = osteoarthritis; PBO = placebo.

Protocol SM04690-OA-07
Biosplice Therapeutics, Inc.

AM02V00
04 May 2021

**Inclusion/
Exclusion
Criteria:**

Criteria for Inclusion:

1. Completion of study SM04690-OA-11
2. Compliance with procedures in study SM04690-OA-11, in the opinion of the Investigator
3. Fully understanding study requirements and willingness to comply with study visits and assessments
4. Understanding and signing of the informed consent form (ICF) prior to any study-related procedures

Criteria for Exclusion:

1. Any condition that, in the opinion of the Investigator, constitutes a risk or contraindication for participation in the study or that could interfere with the study objectives, conduct, or evaluation
2. Any contraindications for an intra-articular (IA) injection in the target knee in the opinion of the Investigator
3. Any known reason identified by the Investigator or Sponsor that the subject may not be compliant with study visits or may no longer be an appropriate candidate for the study (e.g., planned surgery of the pelvis/hip, knee, ankle, or foot, knee replacement during the parent study, planning to move away from the research site, or initiation of a prohibited concomitant medication including, but not limited to, IA injection of glucocorticoids, hyaluronic acid derivatives, platelet-rich plasma, stem cell therapies, or other agents with therapeutic intent into the target knee)
4. Participation in a clinical research trial (other than the prior SM04690-OA-11 study) that included the receipt of an investigational product (IP) or any experimental therapeutic procedure within 12 weeks before any study injection, or planned participation in any such trial
5. Current or pending disability claim, workers' compensation, or litigation(s) that may compromise response to treatment

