10.4.3 ANALYSIS OF EFFICACY ENDPOINT(S)

Change over time through Visit 3E in mJSW, pain NRS, WOMAC Pain, WOMAC Function, and WOMAC Total will be characterized using mixed-effects models for repeated measures (MMRM). The models will estimate change from parent-study baseline with treatment, visit, treatment \times visit interaction, and parent-study baseline value as covariates. Unadjusted 95% confidence intervals and *P* values will be reported. The potential confounding effect of change in NSAID/acetaminophen usage on the treatment effect will be considered for sensitivity analysis.

ANCOVA will be used to analyze the change in SF-36 domain scores and summary component scores through Visit 3E. Change will be assessed from parent-study baseline between the active and placebo treatment groups. The models will be adjusted for parent-study baseline. Unadjusted 95% confidence intervals and *P* values will be reported.

PASS will be analyzed using logistic regression. Logistic regression will also be used to compare the proportion of Outcome Measures in Rheumatology Clinical Trials (OMERACT)-Osteoarthritis Research Society International (OARSI) responders and “strict” responders ([Pham et al. 2003](#)) between treatment groups through Visit 3E, as well as proportion of subjects achieving a 20%, 50%, and 70% improvement.

Maintenance of LOR’s effects on pain and function of the target knee will be characterized by summarizing likelihood of response in pain NRS, WOMAC Pain, and WOMAC Function in the current study for those subjects that had a response in the parent study. Response will be characterized as a 20%, 50%, and 70% improvement.

After all subjects have received LOR at Visit 3E, all further efficacy analyses will be descriptive in nature.

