6. The least squares estimate of improvement from parent-study baseline in medial joint space width in the target knee at Visit 6E (Week 100) is greater for subjects who received “Placebo-LOR”, “LOR-LOR” and All (pooled “Placebo-LOR” and “LOR-LOR”) subjects compared to test values (carry forward and progression assumptions) derived from the change from baseline estimates from the Placebo group at Visit 3E (Week 48)

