9.6.5.2 Analysis

For each group of interest described in Section 9.6.5.1, we will estimate an mJSW baseline-adjusted ANCOVA at Visit 6E (Week 100) and test the difference against two test values:

- Carry-forward (i.e., no change) assumption test value will use the mJSW baseline-adjusted ANCOVA estimate at Visit 3E (Week 48) from the Placebo group.
- Progression (i.e., worsening) assumption test value will use the mJSW baseline-adjusted ANCOVA estimate at Visit 3E (Week 48) from the Placebo group extrapolated to a presumption of continued Placebo use.

Analysis will be performed using the parent and OA-07 study baselines.

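### The Week 100 tests compare each group with a placebo Visit 3E estimate but make no provision for that estimate's sampling error, its multiplication under extrapolation, or the shared placebo subjects

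*SAP*

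**What the plan says.** SAP 9.6.5.1 defines three groups for the open-label phase: Placebo-LOR, LOR-LOR, and the two pooled. For each, 9.6.5.2 states that "we will estimate an mJSW baseline-adjusted ANCOVA at Visit 6E (Week 100) and test the difference against two test values". The carry-forward "test value will use the mJSW baseline-adjusted ANCOVA estimate at Visit 3E (Week 48) from the Placebo group". The progression value is the same estimate "extrapolated to a presumption of continued Placebo use", with no extrapolation rule given. The section adds: "Analysis will be performed using the parent and OA-07 study baselines".

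SAP 9.1 and 9.2 (item 6 of the other hypotheses) and Appendix 2 describe the comparator in the same way, as "test values (carry forward and progression assumptions) derived from the change from baseline estimates from the Placebo group at Visit 3E". SAP 3.2.4 item 3 also lists pain NRS, WOMAC Pain and WOMAC Function against such values, although 9.6.5.2 covers mJSW only.

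Protocol 10.4.3 planned otherwise: "After all subjects have received LOR at Visit 3E, all further efficacy analyses will be descriptive in nature". SAP section 13 declares the departure, attributes it to a study team decision, and points to a section 9.4.4 that does not exist in the SAP; the analysis is in 9.6.5.

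**The concern.** The comparator is a sample mean from the placebo arm. A test against a value ordinarily uses only the standard error of the tested mean. Three things are then left out:

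- the sampling variance of the placebo Visit 3E estimate;
- the factor k² by which extrapolation multiplies that variance;
- the covariance that arises because the placebo subjects at Visit 3E are the Placebo-LOR subjects at Visit 6E, and also part of the pooled group.

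There is no concurrent control after Visit 3E, so these are the Week 100 tests of LOR against a placebo-derived benchmark. Three groups, two test values and two baselines give 3 × 2 × 2 = 12 mJSW tests in each analysis set. If the omitted terms matter, the P values and intervals would misstate the evidence that LOR does better than continued placebo.

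The extrapolation factor is also open. If placebo joint space narrows over time, a larger k gives a more negative test value, which is easier for LOR to beat. SAP 4.4 says the sponsor was unblinded once the parent-study database was locked, so k should be fixed in writing.

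**Working it through.** The documents state no standard error, alpha, power or error rate for these tests, so there is no plan figure to reproduce.

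**Time scale and k (linear extrapolation assumed).** Visit 1E falls at parent Week 56, with a window of up to 6 weeks more (Protocol 7.3.1).

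- Parent baseline: Visit 3E is at 56 + 48 = 104 weeks and Visit 6E at 56 + 100 = 156 weeks. k = 156/104 = 1.5, or 162/110 = 1.47 with the 6-week gap.
- OA-07 baseline: there is no Visit 1E radiograph, and the Figure 1 footnote says "X-ray is performed at Week 52 of the parent study". Visit 3E is then 4 + 48 = 52 weeks after the baseline film and Visit 6E is 4 + 100 = 104. k = 104/52 = 2.0, or 110/58 = 1.90 with the 6-week gap. Nominal extension weeks would give 100/48 = 2.08.
- Carry-forward: k = 1.

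**Assumptions the documents do not supply.** Two-sided 5%, 1:1 allocation, n per arm at Visit 3E, and within-subject residual correlation r between Visits 3E and 6E of 0.6 to 0.8. Let s be the ratio of Visit 6E SD to Visit 3E SD, g = s² the variance ratio, and f the fraction of Visit 3E subjects retained to Week 100.

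**Variance ratio VR (true variance over the variance used by a fixed-value test).** The null is that the group's true Visit 6E mean equals k times the true placebo Visit 3E mean.

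- LOR-LOR (independent of placebo): VR = 1 + k²f/g
- Pooled, full retention: VR = (s²/2 + k² − k·r·s)/(s²/2)
- Placebo-LOR, full retention: VR = (s² + k² − 2k·r·s)/s²
- Type I error = 2 × [1 − Φ(1.96/√VR)]

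n cancels, so a larger trial does not help.

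**Worked example.** LOR-LOR, k = 2, f = g = 1: VR = 1 + 4 = 5, 1.96/√5 = 0.877, error 38.1%. With f = 0.6 and g = 2: VR = 1 + 4 × 0.3 = 2.2, 1.96/√2.2 = 1.321, error 18.6%.

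**Results (ranges run over r = 0.6 to 0.8)**

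| Group and case | k = 1 | k = 1.5 | k = 2 |
|---|---|---|---|
| LOR-LOR, equal SD, full retention | 16.6% | 27.7% | 38.1% |
| LOR-LOR, s = 1.5, full retention | 10.3% | 16.6% | 24.0% |
| LOR-LOR, f = 0.6, g = 2 | 8.6% | 13.0% | 18.6% |
| Pooled, equal SD | 9.8–14.4% | 26.6–30.8% | 41.6–44.6% |
| Pooled, s = 1.5 | 3.1–6.0% | 9.8–14.4% | 20.8–25.4% |
| Placebo-LOR, equal SD | 0.2–2.8% | 3.4–10.4% | 14.4–22.4% |
| Placebo-LOR, s = 1.5 | 0.1–1.5% | 0.2–2.8% | 1.5–7.1% |

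With equal SDs, Placebo-LOR carry-forward has VR = 2 − 2r, so it is conservative whenever r exceeds 0.5 and exactly nominal at r = 0.5. With 2:1 allocation to LOR, LOR-LOR rises to 25.8% (k = 1) and 51.4% (k = 2).

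A simulation of the ANCOVAs (200 per arm, 6,000 runs per setting, equal SDs, full retention) agrees: for LOR-LOR it gave 16.3–16.8%, 27.6–29.4% and 37.2–38.3%.

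**The case against.** - **The SAP does not say the test value is error-free.** That is correct. A reader might infer that it does, but 9.6.5.2 is silent on how the standard error is formed. What stands is that no provision is stated, and a test against a value is naturally read as a one-sample test.
- **Every input is assumed.** Also correct. Item 6 of the hypotheses in 9.1 and 9.2 is worded directionally, although SAP 7.1.2 is two-sided. Counting only false claims of benefit halves the rates: 8.3%, 13.8% and 19.0% for LOR-LOR in the base case, against a nominal 2.5%. The relative inflation is similar.
- **Inflation of 10% to 45% might be inferred for both LOR-LOR and pooled throughout.** The working does not support that. Pooled carry-forward is near or below nominal at s = 1.5, and LOR-LOR carry-forward can fall to 8.6%.
- **These might be taken for the only open-label efficacy inference.** They are not. The PASS regression (9.6.3) and the concordance analysis (9.6.4) also reach Visit 6E.
- **The FAS version compares Week 100 survivors with all placebo subjects at Week 48.** SAP 9.6 repeats the analyses on the Completers Analysis Set (6.5), which partly deals with this.
- **A factor of 100/48 might be presumed.** No text says it will be used. Against 2.0 it moves LOR-LOR only from 38.1% to 39.6%. The gap is that k is not defined at all.
- **The departure from the protocol is disclosed.** It is, in SAP section 13, but disclosure does not supply a standard error.

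**Conclusion.** The point holds as a gap that should be fixed. For LOR-LOR the direction is certain under a fixed-value reading: its subjects are independent of the placebo estimate, so the omitted variance is always positive. The pooled progression tests are inflated in every case tabulated. Pooled carry-forward runs from about 3% to 14%, so even its direction depends on the SDs and the correlation. Placebo-LOR carry-forward is generally conservative, and Placebo-LOR progression can go either way. The percentages are illustrations resting on assumed alpha, allocation, SDs, correlation, retention and linear extrapolation.

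A reader might infer that the trial's main efficacy conclusions are at risk. They are not: SAP 3.2.4, 9.1 and 9.2 class these as other endpoints and hypotheses, and the primary and secondary analyses in 9.4 and 9.5 do not use the test values.

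**What to change.** In SAP 9.6.5.2 and Appendix 2:

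- Define the estimate as LSmean(group, Visit 6E) − k × LSmean(placebo, Visit 3E). Its standard error should include the placebo estimate's variance and the within-subject covariance.
- Name one method: a joint repeated-measures model for Visits 3E and 6E, or a subject-level bootstrap that re-estimates the test value in each resample. They are not interchangeable under dropout, because the joint model uses Visit 3E data from subjects without a Visit 6E film and a bootstrap of available-data ANCOVAs does not.
- State k in advance on the radiograph time scale: 1 for carry-forward, about 1.5 from parent baseline, and about 2.0 from OA-07 baseline.
- Label the result a non-randomised comparison.

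The cost is a few sentences and one model or bootstrap. The downside is wider, less favourable intervals for LOR-LOR and for the pooled progression tests. With 1:1 allocation, equal SDs, full retention and r = 0.7, the standard error is multiplied by √VR. For k = 1, 1.5 and 2 that is 1.41, 1.80 and 2.24 for LOR-LOR, and 1.26, 1.84 and 2.49 for pooled. For Placebo-LOR it is 0.77, 1.07 and 1.48, so its carry-forward interval narrows.

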9.6.6 Subgroup Analysis

The efficacy analyses described in Sections 9.4, 9.5, and 9.6 will be further analyzed by KL Grade.

10. SAFETY AND TOLERABILITY ANALYSIS

The analysis of safety outcome measures will be performed on the Safety Analysis Set. No formal statistical tests are planned for safety.

10.1 Adverse Events

Data regarding AEs will be collected in this study. As this is an extension trial, AE collection will continue from the parent study, ongoing AEs at the end of the parent study will continue to be monitored, and new AEs that occur during this study will be recorded. Changes to ongoing AEs that occur after the parent-study EOS visit will not be recorded in the parent study. AEs will be assessed through the Termination Visit. AEs will be presented in summary tables depicting the number and percent of unique subjects experiencing each AE and the number of AEs by the following analysis periods: (1) AEs that started prior to a Second OA-07 Injection (end of the single-blind, placebo-controlled period of the study; including all AEs for subjects who only received the First OA-07 Injection to End of Study, EOS), (2) on or after Second OA-07 Injection to prior to Third OA-07 Injection (including all AEs for subjects who received the Second OA-07 Injection to EOS), and (3) on or after Third OA-07 Injection to EOS. The following summaries will be provided:

- All AEs and all SAEs by severity and relationship to study product
- AEs by highest degree of seriousness, severity, and relationship to study drug
- AEs by MedDRA system organ class and preferred term
- SAEs sorted by preferred term incidence
- AEs with incidence of greater than 2% in the active treatment group sorted by preferred term incidence
- Target-knee-related AEs and SAEs sorted by preferred term incidence
- AEs leading to study withdrawal, discontinuation of study drug, or death
- SAEs in subjects diagnosed with COVID-19

If an AE start or end date is incomplete, it will be imputed in a way that assumes maximum exposure time (see table in [Appendix 3 – Partial Date Imputation](#)). Separate subject-level listings will be provided for all AEs and all SAEs.

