7.3.2 STUDY VISITS

Visit 2E

Visit 2E should occur 24 weeks after the Visit 1E injection with a window of \pm 4 weeks.

Confidential

The following procedures and assessments will be performed at Visit 2E:

- Pain NRS assessment
- WOMAC questionnaire
- Collection of AE and concomitant procedures/therapies/medication data
- Assessment of NSAID/acetaminophen usage
- Knee examination
- Weight measurement
- Vital sign measurements (pulse rate and blood pressure)
- Venipuncture and collection of samples for clinical laboratory tests
- Radiograph – bilateral in weight-bearing fixed flexion position, PA view X-ray

Visit 3E

Visit 3E should occur 48 weeks after the Visit 1E injection with a window of ± 4 weeks. Subjects should fast for 8 hours prior to this visit.

The following procedures and assessments will be performed at Visit 3E:

- Pain NRS assessment
- WOMAC questionnaire
- PASS assessment
- SF-36
- Collection of AE and concomitant procedures/therapies/medication data
- Assessment of NSAID/acetaminophen usage
- Pregnancy test (urine-based) in WOCBP
- Physical examination
- Knee examination
- Weight measurement
- Vital sign measurements (temperature, pulse rate, and blood pressure)
- Venipuncture and collection of samples for clinical laboratory tests and biomarkers
- Radiograph – bilateral in weight-bearing fixed flexion position, PA view X-ray
- IA injection of LOR into the target knee; **the target knee must be the same as the knee injected in the parent study.**

Visit 4E (Phone Visit)

The Visit 4E phone visit should occur on Week 52 (with a window of ± 7 days). Sites will contact subjects to collect AE and concomitant procedures/therapies/medication data.

Visit 5E, 7E, 9E, etc.

These visits should occur on Weeks 74, 126, 178, etc. with a window of ± 4 weeks.

The following procedures and assessments will be performed at these visits:

- Pain NRS assessment
- WOMAC questionnaire
- Collection of AE and concomitant procedures/therapies/medication data
- Assessment of NSAID/acetaminophen usage
- Knee examination
- Radiograph – bilateral in weight-bearing fixed flexion position, PA view X-ray

Visit 6E, 8E, 10E, etc.

These visits should occur on Weeks 100, 152, 204, etc. with a window of ± 4 weeks.

The following procedures and assessments will be performed at these visits:

- Pain NRS assessment
- WOMAC questionnaire
- PASS assessment
- SF-36
- Collection of AE and concomitant procedures/therapies/medication data

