8.3 TIME PERIOD AND FREQUENCY FOR EVENT ASSESSMENT AND FOLLOW-UP

The reporting period for AEs starts immediately following the parent-study EOS visit and ends after the final study visit.

AEs will be followed until the subject's last visit or resolution, whichever comes first. For subjects who discontinue from the study within 30 days of their last study injection, AEs that are ongoing at the subject's last visit will be followed for 30 days after administration of the last dose or until resolution, whichever comes first. Resolution is defined as the return to baseline status or stabilization of the condition. SAEs and selected AEs identified by the Investigator or the Sponsor to warrant further follow-up that are ongoing at a subject's last visit will be followed until resolution.

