3. STUDY OBJECTIVES AND ENDPOINTS

3.1 Study Objective

The objective of this study was to evaluate the safety and efficacy of a second year as well as long-term use of LOR in subjects with knee OA.

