4.1 Changes to Overall Study Design and Plan

The sponsor elected to administratively terminate this study. All active subjects were requested to continue the study until they completed Visit 6E (Week 100); subjects injected at this visit were followed-up via phone call 10 days (+/-3 days) for safety data collection. Subjects that had already completed their Visit 6E (Week 100) were asked to schedule a termination visit as soon as possible. All procedures for the termination visit should be performed; however, as provided in the protocol, an additional X-ray was not required if a subject had an X-ray taken within the 12 weeks prior to their termination visit.

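### Adverse events are tabulated as crude percentages by injection period, but period 3 can last only 7-13 days, so its percentages are not comparable with those of periods 1 and 2

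*SAP*

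**What the plan says.** SAP 10.1 summarises AEs as the "number and percent of unique subjects experiencing each AE and the number of AEs by the following analysis periods". The periods are:

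- Period 1: "AEs that started prior to a Second OA-07 Injection". It runs to end of study (EOS) for subjects with only one OA-07 injection.
- Period 2: "on or after Second OA-07 Injection to prior to Third OA-07 Injection". It runs to EOS for subjects with no third injection.
- Period 3: "on or after Third OA-07 Injection to EOS". No length is fixed.

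The schedule sets the first two lengths. Protocol 7.3.2 states that "Visit 3E should occur 48 weeks after the Visit 1E injection", and the next injection falls at Visit 6E, Week 100. SAP 4.1 then changes what happens after Visit 6E. Following the sponsor's decision to terminate, "subjects injected at this visit were followed-up via phone call 10 days (+/-3 days) for safety data collection". Subjects already past Visit 6E were asked to arrange a termination visit promptly.

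SAP 12.2 provides exposure only as a listing by subject. SAP 10 plans no formal safety tests. SAP 10.1 does not say whether a period's percentages use the whole Safety Analysis Set or only the subjects who entered that period. The aim in SAP 3.1 is to "evaluate the safety and efficacy of a second year as well as long-term use of LOR".

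**The concern.** A crude percentage depends on how long subjects are watched as well as on how often events occur. When one column covers about a year and another covers as little as a week for some of its subjects, the columns do not measure the same thing. The analysis is descriptive, so no test would go wrong. The tables will still be read across, and a low period 3 figure could pass for good tolerability of a third OA-07 injection when it reflects short observation.

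This matters because long-term safety is a stated objective, and the AE endpoint in SAP 3.2.3 stops before the second OA-07 injection. The period 2 and period 3 tables are therefore the only AE summaries by period after Visit 3E. If the denominator is the whole Safety Analysis Set, subjects who never had a third injection would lower the period 3 percentages further.

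**Working it through.** The documents give no AE rate, no count of subjects entering period 3 and no sample-size calculation bearing on safety, so there is no stated figure to reproduce. The period lengths come from the documents. The event rates and follow-up mixtures are assumptions.

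**Period lengths**

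- Period 1: 48 weeks nominal from the Visit 1E injection, 44-52 with the visit window. AE reporting starts at the parent-study EOS visit and Visit 1E may be up to 6 weeks later, so the maximum is 52 + 6 = 58 weeks.
- Period 2: 100 − 48 = 52 weeks nominal. With both windows it is 96 − 52 = 44 to 104 − 44 = 60 weeks.
- Period 3, injected at Visit 6E with the safety call: 10 ± 3 = 7-13 days. This takes the call as the last safety contact; SAP 4.1 describes no later one.
- Period 3, already past Visit 6E: not stated.

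The ratio of period 2 to period 1 is 52/48 = 1.08. The ratio of period 2 (364 days) to period 3 for subjects followed by the call is 364/13 = 28 to 364/7 = 52.

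**Effect of length alone, 45% assumed annual incidence**

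With a constant hazard, λ = −ln(1 − 0.45)/364 = 0.001642 per day, and the percentage with an event over t days is 1 − exp(−λt).

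| Observation time | Crude percent |
|---|---|
| 336 days (period 1) | 42.4% |
| 364 days (period 2) | 45.0% |
| 7 days | 1.1% |
| 10 days | 1.6% |
| 13 days | 2.1% |

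The underlying rate is the same in every row: 0.001642 × 365.25 × 100 = 60.0 per 100 subject-years.

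**Mixed follow-up in period 3, same hazard**

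The percentage is s × 1.63% + (1 − s) × p, where s is the share of subjects with 10 days and p is the incidence over the longer follow-up (25.8% at 26 weeks, 45% at 52 weeks).

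| Share with 10 days | Follow-up of the rest | Period 3 percent | 45% divided by it |
|---|---|---|---|
| 100% | none | 1.6% | 27.6 |
| 75% | 26 weeks | 7.7% | 5.9 |
| 50% | 52 weeks | 23.3% | 1.9 |
| 25% | 52 weeks | 34.2% | 1.3 |

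**Other event rates, all of period 3 at 10 days**

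Here λ = −ln(1 − p48)/336, where p48 is the assumed 48-week incidence.

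| p48 | Period 1 | Period 2 | Period 3 (7-13 days) | Rate per 100 subject-years |
|---|---|---|---|---|
| 10% | 10.0% | 10.8% | 0.31% (0.22-0.41%) | 11.45 |
| 30% | 30.0% | 32.0% | 1.06% (0.74-1.37%) | 38.77 |

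One hundred subjects contribute about 92 subject-years in period 1 (100 × 336/365.25), 99.7 in period 2 and 2.7 in a 10-day period 3.

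**The case against.** Much of the case on the other side stands, and it limits the point.

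- A reader might infer that LOR will look safer with each further injection. The lengths do not support that. Periods 1 and 2 are similar, and length alone raises period 2 slightly (10.8% against 10.0%). Any artefact is a drop at period 3 only.
- A reader might attach one inflation factor to the drop, such as six-fold. That rests on one invented split, 75% at 10 days and 25% at 26 weeks. At 45% annual incidence the mixtures above run from about 1.3-fold to 28-fold, and the documents do not say which applies.
- A reader might infer that the table of AEs above 2% incidence would lose terms in period 3. SAP 10.1 does not say that the threshold applies within periods. Preferred-term and target-knee tables are planned without a threshold.
- A reader might see a conflict with Protocol 8.3, under which certain AEs "will be followed for 30 days after administration of the last dose or until resolution". That text concerns AEs ongoing at the last visit in subjects who discontinue within 30 days of an injection. A call to collect safety data does not contradict it.
- Repeat exposure does not rest on period 3 alone. LOR-LOR subjects had LOR in the parent study and at Visit 1E, so period 2 follows a further LOR injection for about 52 weeks. Keeping period 3 separate also prevents it from diluting period 2.
- Person-time rates have an artefact of their own. If 2% of subjects react in the first week after every injection, the crude percentage correctly shows 2% each time. The rate shows 2/0.997 = about 2 per 100 subject-years over 364 days, but 2/0.0274 = about 73 over 10 days.

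The last objection is a reason to show rates beside percentages, not to omit follow-up time. None of these points makes the period 3 percentages comparable.

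**Conclusion.** The point holds in limited form. As written, the plan yields period 3 crude percentages that are not comparable with periods 1 and 2 and can understate AEs that accrue over time. The difference in observation time is 28- to 52-fold against period 2 for subjects followed only by the 7-13 day call. The effect on the reported percentages cannot be fixed from the documents: at an assumed 45% annual incidence and constant hazard, the scenarios shown give from 1.6% to about 34% in period 3 with no change in the true rate. Reactions clustered in the first days after injection would be largely captured, so the understatement concerns later events.

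The LOR versus placebo comparison in period 1 is not affected, because both arms follow the same schedule. This is an inexpensive improvement to the safety tables and does not invalidate the safety analysis.

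**What to change.** Amend SAP 10.1 as follows:

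1. State the denominator for each period as subjects entering that period.
2. Show total subject-years and median follow-up by period and treatment sequence.
3. Give exposure-adjusted incidence rates beside the crude percentages, not in place of them.
4. Add a descriptive table of AEs with onset on Days 1-7 after each OA-07 injection. The earliest permitted call covers this window.
5. Footnote that period 3 crude percentages are not comparable with periods 1 and 2.

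Two further footnotes are needed. Rates assume a roughly constant hazard and will inflate early injection reactions in a very short period 3. The Days 1-7 window is also ascertained at different distances: the next scheduled contact is the Week 24 visit after the first injection, the Week 52 call (about 4 weeks later) after the second, and the 7-13 day call after the third for subjects so followed. Recall may therefore differ.

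The cost is SAP wording, some columns and one short table, built from injection, AE onset and last-contact dates already held. No new data collection is required.
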